7.1 LIMITED WAIVER OF AUTHORIZATION

Potential research subjects will be identified by a member of the patient's treatment team, the protocol investigator, or research team at Memorial Sloan-Kettering Cancer Center (MSKCC). If the investigator is a member of the treatment team, s/he will screen their patient's medical records for suitable research study participants and discuss the study and their potential for enrolling in the research study. Potential subjects contacted by their treating physician will be referred to the investigator/research staff of the study.

The principal investigator may also screen the medical records of patients with whom they do not have a treatment relationship for the limited purpose of identifying patients who would be eligible to enroll in the study and to record appropriate contact information in order to approach these patients regarding the possibility of enrolling in the study. For the majority of the potential research participants, most will have a treatment relationship with the investigators and consenting professionals listed on the front sheet of protocol. We plan to maintain a screening log for all patients considered for this study.

During the initial conversation between the investigator/research staff and the patient, the patient may be asked to provide certain health information that is necessary to the recruitment and enrollment process. The investigator/research staff may also review portions of their medical records at MSKCC in order to further assess eligibility. They will use the information provided by the patient and/or medical record to confirm that the patient is eligible and to contact the patient regarding study enrollment. If the patient turns out to be ineligible for the research study, the research staff will destroy all information collected on the patient during the initial conversation and medical records review, except for any information that must be maintained for screening log purposes.

In most cases, the initial contact with the prospective subject will be conducted either by the treatment team, investigator or the research staff working in consultation with the treatment team. The recruitment process outlined presents no more than minimal risk to the privacy of the patients who are screened and minimal PHI will be maintained as part of a screening log. For these reasons, we seek a (partial) limited waiver of authorization for the purposes of (1) reviewing medical records to identify potential research subjects and obtain information relevant to the enrollment process; (2) conversing with patients regarding possible enrollment; (3) handling of PHI contained within those records and provided by the potential subjects; and (4) maintaining information in a screening log of patients approached (if applicable).

8.1 PRETREATMENT EVALUATION

To be completed within 28 days of starting Cycle 1 Day1 (unless otherwise indicated):

- Signed informed consent for study participation
- History and physical examination including height, weight, vital signs (temperature, pulse rate, respiratory rate, blood pressure, pulse oximetry), performance status (ECOG), and review of pathology and concomitant medications: medications taken within 28 days of starting Debio 1347 and fulvestrant
- Urine or serum pregnancy test for all women of childbearing potential. If the test result is positive related to pregnancy, the patient will not be allowed to participate in this study
- CBC with differential and platelet count
- Complete metabolic panel (sodium, potassium, chloride, bicarbonate, BUN, creatinine, glucose, total protein, albumin, bilirubin, alkaline phosphatase, AST, ALT, calcium)
- Magnesium

- Phosphorous
- γ GTP
- CPK
- CRP
- Uric Acid
- LDH
- Calcium regulating hormones (whole-PTH, 1,25(OH)2D, PTHrP)
- PT/INR & aPTT
- Serology for HepBsAg, HepBcAb, HIV and hepatitis C antibody (negative test acceptable prior to screening period)
- Tumor markers: CEA and Ca 15-3
- Urinalysis including urinary protein, blood, glucose, urobilinogen, pH, sediment, creatinine, calcium (CA), phosphate
- 12-lead Electrocardiogram (EKG)
- ECHO
- Complete ophthalmologic examination. The examination will be interpreted by a qualified ophthalmologist, including visual acuity testing, slit-lamp ophthalmoscopy and indirect ophthalmoscopy.
- CT scan with contrast (chest, abdomen and pelvis). If patient is unable to receive CT contrast, or the abdominal/pelvic target lesion is indeterminate on CT scan, then MRI with contrast (abdomen and pelvis) plus CT chest without contrast may be performed.
- A baseline brain MRI or CT scan with contrast (the same method of imaging done at baseline should be done throughout the study at indicated time points) is required only for patients with a history of brain metastases
- Research blood samples: for PK and cfDNA as detailed in section 12.0
- Baseline tumor biopsies will be obtained during screening for all patients enrolled in the study

9.1 TREATMENT/INTERVENTION PLAN

This is an open-label, single institution, phase Ib/phase II non-randomized trial that evaluates the safety, tolerability and anti-tumor activity of fulvestrant and Debio 1347 in patients with ER+/HER2- metastatic breast cancer (MBC) that are FGFR-amplified (as confirmed by a CLIA certified laboratory).

The phase I portion of this trial will evaluate 2 dose cohorts (dose level 1 (starting dose level) 80mg Debio 1347, and dose level -1, 60mg Debio 1347). Fulvestrant will be administered at standard doses. Only the dose of Debio 1347 will be de-escalated as per section 4.1.

Phase 2 portion: The phase 2 portion will be comprised of an optimal Simon two-stage design to determine the efficacy of Debio 1347 plus fulvestrant (N: 18 in the first stage with possibility of going on to 43 if 3 out of the first 18 have a CBR \geq 24 weeks). The dosage in the phase 2 portion will be the MTD/RP2D determined in the phase 1b portion (**80mg daily**), except that concomitant prophylaxis for hyperphosphatemia will not be required.

1 cycle: 28 days. Patients will be on treatment until progression of disease or unacceptable toxicity.

9.1 Concomitant Medications

Administration of concomitant when administered between the date of informed consent signature and the last visit (including follow-up) will be recorded.

9.1.1 Permitted Concomitant Medication

Supportive therapies against pain, nausea, vomiting, constipation and diarrhea, and granulocyte colony-stimulating factors (G-CSF) are allowed as per the Investigator's decision. Since drugs that alter gastric pH (e.g., proton pump inhibitors, histamine receptors antagonists, antacids) may interfere with the absorption of Debio 1347, they should be administered at least 2 hours after Debio 1347 administration.

Treatment of pain should be done according to severity and recommended drugs. Study-specific guidelines will be provided separately.

Concomitant radiotherapy may only be given for the control of bone pain or as indicated to 30% of the bone marrow. Irradiated lesions will not be evaluable for response. Radiotherapy should start no sooner than 24 hours after the previous dose of Debio 1347, and study treatment may be resumed with the resolution of any radiation toxicity to \leq grade 1.

Any other medication necessary for the well-being of the patient (with the exception of those mentioned as prohibited/excluded concomitant medications, see Section below) may be given at the Investigator's discretion. Particular attention should be paid to treatment that could influence the intended effects or mask side effects of treatment.

9.1.2 Excluded Concomitant Medications

Subjects must be instructed not to take any medications, including over-the-counter products, without first consulting with the investigator.

The following medications are considered exclusionary during the study. The Principal Investigator must be notified if a subject receives any of these during the study.

- Any investigational anticancer therapy.

- Any concurrent chemotherapy, immunotherapy, or biologic therapy. Note: concurrent use of bone-directed therapies (such as bisphosphonates or denosumab) is permitted.
- Other antineoplastic agents are prohibited except GnHR agonists and GnHR antagonists for premenopausal women.
- Concurrent use of hormones for non-cancer-related conditions (e.g., insulin for diabetes) is acceptable.
- Immunosuppressive medications including, but not limited to systemic corticosteroids (>10 mg/day prednisone or equivalent), methotrexate, azathioprine, and tumor necrosis factor alpha (TNF- α) blockers. \ In addition, use of inhaled and intranasal corticosteroids is permitted.
- Fibroblast growth factors injections, cosmetics containing FGF.
- High dose systemic steroids, calcitonin preparations, active Vitamin D3 preparations, estrogen preparations, selective estrogen receptor modulators, Vitamin K2 preparations, parathyroid hormones, phosphorus absorbers

In nonclinical studies, Debio 1347 has been seen to affect the cornea. Since corneal disorders may occur when contact lenses are being worn, and the use of Debio 1347 may exacerbate these symptoms, caution should be exercised when using Debio 1347 in a patient wearing contact lenses, and the patient should be monitored.

Although the possibility of Debio 1347 affecting cardiac function in nonclinical studies is low, caution should be exercised when using Debio 1347 with drugs with a known risk of QTc prolongation (see Arizona CERT database at website <http://www.crediblemeds.org/>).

The hepatic oxidative metabolism of Debio 1347 has been shown in vitro to be mainly mediated by CYP 4F3b, with no or only minor contribution of other metabolic enzymes. Furthermore, according to bi-directional permeability experiments in Caco-2 cells, Debio 1347 is not a substrate of P-glycoprotein (P-gp) or breast cancer resistance protein (BCRP) efflux transporters. Therefore, based on current knowledge, Debio 1347 appears to have a low risk of being victim of PK interaction from other drugs. In contrast, as per in vitro results available so far and Debio 1347 plasma exposure achieved in patients, Debio 1347 is considered at possible risk of perpetrating drug-drug interactions through CYP3A inhibition, CYP3A induction (some transporters such as P-gp might also be co-induced), CYP1A2 repression, or inhibition of several transporters (P-gp, BCRP, multidrug and toxin extrusion protein 1 [MATE1], organic cation transporter 2 [OCT2]; bile salt export pump [BSEP] is also inhibited).

The clinical impact of these in vitro observations is not known. While patients are not precluded from receiving any drugs based upon the potential for a PK drug interaction, patients who are taking concurrent drugs that are known substrates of either CYP3A, CYP1A2, P-gp, BCRP, MATE1 or OCT2 should be carefully monitored.

Notably, due to the irreversible nature of CYP3A inhibition by Debio 1347 and also its in vitro potential for enzyme induction, it should be noticed that the potential for drug-drug

interactions with CYP3A substrates (and possibly also with P-gp substrates) is time-dependent; it may increase with time as patients continue to take Debio 1347, and it may persist for some days after Debio 1347 discontinuation.

A list of drugs that are sensitive or narrow-therapeutic-range substrates of CYP3A, CYP1A2, and substrates of P-gp, BCRP, MATE1 or OCT2 can be consulted in:

- Flockhart DA. Drug Interactions: Cytochrome P450 Drug Interaction Table. Indiana University School of Medicine (2007): <http://medicine.iupui.edu/clinpharm/ddis/table.aspx>, and
- <http://www.fda.gov/Drugs/DevelopmentApprovalProcess/DevelopmentResources/DrugInteractionsLabeling/ucm093664.htm>

If treatment with a prohibited medication is necessary, the patient will be withdrawn from the study.

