9.2.1 Hyperphosphataemia prevention

- All treated patients should receive adequate instructions concerning dietary phosphate restriction. The main natural sources of phosphate are:
 - Dairy products (milk, cheese, ice-cream, yogurt)
 - Meat
 - Dried beans
 - Peas
 - Nuts and peanut butter
 - Wholegrains
 - Cola
- During the dose-escalation phase of the debio 1347 trial, only 50% of patients needed to be treated with phosphate chelators. In the expansion phase, three patients did receive prophylactic sevelamer, and there was no clear difference with regard phosphate levels in these patients. In view of the side-effects associated with use of phosphate chelators, prophylaxis *will not be required* in phase 2 portion of the study. Phosphate levels will be measured on cycle 1 D4 (+/-1 day), and treated according to the guidelines provided in section 9.4.2. At the time of this amendment, all patients on the phase 1 cohort were off study.

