9.4.2 Hyperphosphatemia (Phase I)

1. Initial Modifications on Treatment:

Serum phosphorus level	
5.5 – 6.9 mg/dL	
 1. Continue Debio 1347 2. Continue (or increase) sevelamer powder 2400mg TID 3. Add Fosrenol 1g TID 4. Recheck within 7 days

≥ 7 mg/dL	
 1. Hold Debio 1347 2. Continue (or increase) sevelamer powder 2400mg TID 3. Add Fosrenol 1g TID 4. check within 7 days -> resume if Ph < 5.5 and recheck within 7 days of resumption
----------------	---

*If sevelamer is not available or tolerable, alternate phosphate reducing agents or preparations can be utilized.

2. Second Modification on Treatment

Serum phosphorus level	
5.5 – 6.5 mg/dL	
 1. Cont Debio 1347 2. Cont sevelamer powder to 2400mg TID increase Fosrenol to 1.5mg TID 3. recheck within 7 days
6.6-6.9mg/dL	
 1. Cont Debio 1347 2. Cont sevelamer powder to 2400mg TID 3. Cont Fosrenol 1g TID 4. add acetazolamide 250mg BID 5. recheck within 7 days
≥ 7 mg/dL	
 1. Hold Debio 1347 – consider dose reduction 2. Cont sevelamer powder to 2400mg TID 3. increase Fosrenol to 1.5g TID 4. add acetazolamide 250mg BID 5. check within 7 days -> resume if Ph < 5.5

*If sevelamer is not available or tolerable, alternate phosphate reducing agents or preparations can be utilized.

3. Subsequent Modifications:

Serum phosphorus level	
> 5.5 mg/dL-6.9mg/dL	
 1. If not already, maximize regimen to include: sevelamer powder to 2400mg TID fosrenol to 1.5g TID acetazolamide 250mg BID 2. If already maximized, consider dose reduction (without interrupting drug) 3. Recheck within 7 days
≥ 7 mg/dL	
 1. Hold Debio 1347 – dose reduction needed 2. Maximize regimen to include: sevelamer powder to 2400mg TID fosrenol to 1.5g TID acetazolamide 250mg BID

	3. check within 7days -> resume with dose reduction if Ph < 5.5
--	---

*If sevelamer is not available or tolerable, alternate phosphate reducing agents or preparations can be utilized.

- For patients whose phosphorous control improves after Debio 1347 dose reductions, escalation of the phosphorus regimen can be considered at the discretion of the investigator. Subsequent to any such adjustment, phosphorous level should be rechecked within 7 days.

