9.4.3 Hyperphosphatemia (Phase II)

INITIAL TREATMENT MODIFICATION	
Serum Phosphorous Level	Intervention/Modification
5.5 – 6.9 mg/dL	
 Continue treatment with Debio 1347 at current dose AND Start on sevelamer oral POWDER 1200mg three times a day (subjects may use tablets if preferred, but tends to have more gastrointestinal toxicity) Escalate to sevelamer oral POWDER or tablets 2400mg three times a day if tolerated. Reassess serum phosphorus within 7 days
≥ 7 mg/dL	
 Hold treatment with Debio1347 Start sevelamer oral POWDER or tablets 2400mg three times a day Add treatment with lanthanum carbonate (Fosrenol®) 1g three times a day Reassess serum phosphorus level within 7 days: 
 If serum phosphorus level < 5.5 mg/dL, resume Debio 1347 at same dose and recheck within 7 days of resumption
Note:	
 Sevelamer should be preferably taken in the middle of meals Lanthanum carbonate should be taken just after meals Sevelamer and lanthanum must be administered at least 2 hours after or 4 hours before Debio 1347

SECOND TREATMENT MODIFICATION	
Serum Phosphorous Level	Intervention/Modification
5.5 – 6.5 mg/dL	
 Continue treatment with Debio 1347 at a current dose AND Continue sevelamer oral POWDER or tablets 2400mg three times a day Introduce treatment with lanthanum carbonate (Fosrenol®) to 1.0g three times a day or increase to 1.5g three times a day Reassess serum phosphorus level within 7 days
6.6-6.9 mg/dL	
 Continue treatment with Debio 1347 at current dose AND Continue sevelamer oral POWDER or tablets 2400mg three times a day Introduce treatment with lanthanum carbonate (Fosrenol®) to 1.0g three times a day or increase the dose to 1.5g three times a day Add treatment with oral acetazolamide 250mg twice a day Reassess serum phosphorus level within 7 days
≥ 7 mg/dL	
 Hold treatment with Debio 1347 – consider dose reduction Continue sevelamer oral POWDER or tablets 2400mg three times a day Increase treatment with lanthanum carbonate (Fosrenol®) to 1.5g three times a day AND

	
 • Add treatment with oral acetazolamide 250mg twice a day • Reassess serum phosphorus level within 7 days: 
 ◦ If serum phosphorus level < 5.5 mg/dL, resume Debio 1347 with dose reduction

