Note:	
 • Sevelamer should be preferably taken in the mid of meals • Lanthanum carbonate should be taken just after meals • Sevelamer and lanthanum must be administered at least 2 hours after or 4 hours before Debio 1347 • Acetazolamide should be preferably taken just after breakfast and dinner

SUBSEQUENT TREATMENT MODIFICATIONS

Serum Phosphorous Level	Intervention/Modification
5.5 – 6.9 mg/dL	
 • If not already done, maximize regimen to include: 
 ◦ Sevelamer oral POWDER or tablets to 2400mg three times a day ◦ Lanthanum carbonate (Fosrenol®) to 1.5g three times a day ◦ Oral acetazolamide 250mg twice a day • If regimen already maximized, consider dose reduction (without interrupting Debio 1347 assumption) • Reassess serum phosphorus level within 7 days
≥ 7 mg/dL	
 • Hold treatment with Debio1347 – dose reduction needed • Maximize regimen to include: 
 ◦ Sevelamer oral POWDER or tablets to 2400mg three times a day ◦ Lanthanum carbonate (Fosrenol®) to 1.5g three times a day ◦ Oral acetazolamide 250mg twice a day • Reassess serum phosphorus level within 7 days: 
 ◦ If serum phosphorus level < 5.5 mg/dL, resume Debio 1347 with dose reduction
Note:	
 • Sevelamer should be preferably taken in the mid of meals • Lanthanum carbonate should be taken just after meals • Sevelamer and lanthanum must be administered at least 2 hours after or 4 hours before Debio 1347 • Acetazolamide should be preferably taken just after breakfast and dinner

GENERAL RECOMMENDATIONS

- In subjects whose serum phosphorus control improves after Debio 1347 dose reduction, de-escalation of the hyperphosphatemia treatment can be considered at the discretion of the Investigator. Subsequent to any such adjustment, serum phosphorus level should be reassessed within 7 days.
- In case of subjects with hepatic or renal impairment, it is recommended not to change hyperphosphatemia treatment even in the case of Debio 1347 dose reduction.

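### Section 9.1.2 bars phosphorus absorbers without exception while 9.4.3 orders them, so 12.3.3 and 9.5, read literally, could exclude and replace phase 2 patients treated as directed

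*Combined protocol and SAP*

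**What the plan says.** **The prohibition.** Section 9.1.2 lists drugs that are exclusionary while a patient is on study. The last item includes "Vitamin K2 preparations, parathyroid hormones, phosphorus absorbers". The section ends: "If treatment with a prohibited medication is necessary, the patient will be withdrawn from the study". Section 10.1.4, item 7, also gives use of a prohibited drug as a reason for early discontinuation, but there the site contacts the Medical Monitor and the decision is taken with the Sponsor.

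**The instruction.** In the phase 2 ladder of 9.4.3, the first step at 5.5 to 6.9 mg/dL is "Start on sevelamer oral POWDER 1200mg three times a day" with Debio 1347 continued. At 7 mg/dL or more, Debio 1347 is held and sevelamer and lanthanum are both given. Later steps bring lanthanum in at the lower levels too. The phase 1 ladder in 9.4.2 opens with "Continue (or increase) sevelamer powder 2400mg TID" and adds lanthanum.

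**The analysis and replacement rules.** Section 12.3.3 removes from the efficacy population any patient given a concomitant treatment that is not permitted. Section 9.5 replaces phase 2 patients who are not eligible for efficacy evaluation.

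**The concern.** A site cannot obey 9.1.2 and 9.4.3 together. The conflict is more than untidy drafting because the term on which 12.3.3 turns, non-permitted treatment, has to be looked up in 9.1.1 and 9.1.2. Whoever fixes the efficacy population by the letter would find binders on the barred list.

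A patient whose phosphorus rose on Debio 1347, and who was managed as the protocol requires, could then be taken out of the efficacy set and replaced. Membership would depend on a drug effect seen after baseline. If that set is the denominator for clinical benefit, the estimate would describe a selected group. Hyperphosphatemia was the most common adverse event reported for this drug (75% in single-agent dose escalation, section 3.3.4), so the question is likely to arise in practice.

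**Working it through.** **1. Is an exception written anywhere?** Section 9.1.2 states exceptions where they are meant, for example "Other antineoplastic agents are prohibited except GnHR agonists and GnHR antagonists for premenopausal women". It also allows bone-directed therapy and inhaled or intranasal steroids. The phosphorus-absorber item has none. Section 9.1.1 does not supply one: it allows other necessary medication "with the exception of those mentioned as prohibited/excluded concomitant medications". A drug on the barred list is therefore a non-permitted drug.

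**2. Does 12.3.3 limit its own exclusion?** No. Section 12.3.2 removes patients from the dose-finding population only for non-permitted treatments that affect the DLT evaluation. The first condition in 12.3.3 is limited to clinically relevant eligibility violations. The second condition, on concomitant treatment, has no limit.

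**3. Which reading is intended?** The ladders.
- Table 1 in 9.4 sends hyperphosphatemia to 9.4.2 and 9.4.3.
- The DLT definition in 9.3 presupposes phosphorus-lowering therapy.
- Section 9.4.3 keeps patients on Debio 1347 at full binder doses when phosphorus is 5.5 to 6.9 mg/dL: "If regimen already maximized, consider dose reduction (without interrupting Debio 1347 assumption").
- Sections 4.2 and 9.1 waive binder prophylaxis for phase 2, so binders were contemplated as part of study care.

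The same drug list stands among the eligibility exclusions in 6.3, where it makes sense as a baseline restriction.

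**4. Which ladder applies in phase 2?** Section 9.2.1, in describing phase 2, says phosphate will be measured "and treated according to the guidelines provided in section 9.4.2". Table 1 points phase 2 to 9.4.3. The two ladders differ at the first step. At 5.5 to 6.9 mg/dL, 9.4.2 assumes sevelamer is already being taken, sets 2400 mg three times daily and adds lanthanum. Section 9.4.3 starts sevelamer at 1200 mg three times daily without lanthanum. Section 9.2.1 also records that all phase 1 patients were off study at the amendment, so from then on only 9.4.3 matters.

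**5. The plan's design figures, with nobody excluded.** Inputs from section 14.0: n1 = 18, stop if 2 or fewer have clinical benefit; n = 43, positive if 8 or more; rates 10% and 25%.

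P(stop) = Σ C(18,x) pˣ(1−p)¹⁸⁻ˣ for x = 0 to 2.
At p = 0.10: 0.1501 + 0.3002 + 0.2835 = 0.7338 (stated 0.73).
At p = 0.25: 0.1353.

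P(positive) = Σ P(X1 = x) · P(Y ≥ 8 − x) for x = 3 to 18, with Y binomial(25, p).
At p = 0.10: 0.0480 (stated as a 5% level, not exceeded).
At p = 0.25: 0.8003 (stated 80%).

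The design is sound. If binder use never removes a patient, these figures are unchanged.

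**6. How often could the rules meet?** The documents give no rate of binder use at 80 mg with fulvestrant. Section 9.2.1 gives 50% needing chelators in the single-agent dose-escalation part, which covered 10 to 150 mg daily (3.3.4). The 75% is the rate of hyperphosphatemia, not of binder use.

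**The case against.** The strongest reply is that a dosed, step-by-step instruction overrides one item in a general list, so no sensible reader would call protocol-ordered sevelamer non-permitted. As a statement of intent that is right. It does not change the text of 9.1.2 or 12.3.3, and no section reconciles them.

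Two further replies limit the point. Withdrawal is not automatic: 10.1.4 item 7 puts a joint decision with the Sponsor in the way, although the closing sentence of 9.1.2 is unconditional. The link to the primary endpoint is also inferred. Section 14.0 states the rule for 18 and then 43 patients without naming the 12.3.3 population, and the phase 2 line of 9.5 cites no population definition. Section 14.0 does say that safety analyses include patients who are not evaluable for the efficacy endpoint, which makes the inference plausible without settling it.

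A reader might go further and infer that the trial needs far more patients. At 50% binder use, 43/(1 − 0.50) = 86 enrolled for 43 evaluable; at an assumed 25% or 75%, 58 or 172. The documents do not support this as a forecast. It requires the literal reading against evident intent, automatic exclusion, and a rate borrowed from a different setting. Nor do they support a claim of lost power or of bias in a given direction, because nothing is said about whether patients who need binders benefit more or less than others.

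**Conclusion.** The point holds: the text is wrong as written, and severity is low. The prohibition and the ladder contradict each other, and the literal text of 12.3.3 and 9.5 could carry that contradiction into the efficacy population. Under the evident intent the effect on the design is zero.

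The conclusion rests on two assumptions. The first is that phosphorus absorbers, a term the protocol does not define, covers sevelamer and lanthanum; that is its ordinary meaning, and acetazolamide would not fall under it. The second, needed only for the step to the primary analysis, is that clinical benefit is counted in the 12.3.3 population.

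**What to change.** - **9.1.2:** add to the phosphorus-absorber item and to the withdrawal sentence: except phosphate-lowering agents given as directed in 9.4.2/9.4.3.
- **12.3.3:** state that such treatment is permitted, and that it neither removes a patient from the efficacy population nor triggers replacement under 9.5.
- **9.2.1:** change the phase 2 cross-reference from 9.4.2 to 9.4.3.

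The cost is one clarifying amendment, with no extra patients, visits or procedures. It should be made before the efficacy population is fixed.
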